5.2. Criteria for eliminating data from Analysis Sets

Elimination codes are used to identify subjects to be eliminated from analysis. Detail is provided below for each analysis set.

5.2.1. Elimination from Total cohort without subjects with code 900

Code 900 (invalid informed consent or fraudulent data) will be used for identifying subjects eliminated from Total cohort without subjects with code 900.

5.2.2. Elimination from ATP cohort

Code 900 (invalid informed consent or fraudulent data) and code 2010 (Protocol violation linked to the inclusion/exclusion criteria) will be used for identifying subjects eliminated from ATP cohort.

5.3. Important protocol deviation not leading to elimination from Analysis sets

Refer to the Periodic Review of Protocol deviation documents stored in
PPD

6. DENGUE CASE CLASSIFICATION

The following classification of suspected dengue case (SDC) will be used in this study.

6.1. Suspected symptomatic dengue case

As per protocol a suspected symptomatic dengue case was defined by febrile illness with body temperature $\geq 38^{\circ}\text{C}$ measured (by any route) on at least two consecutive days and less than 14 days with or without the presence of other dengue symptoms or signs, without an obvious aetiology unrelated to dengue, based on investigator's judgement.

Note that few cases were reported as suspected symptomatic dengue cases without documentation of fevers. These cases will be ignored from all analyses on symptomatic dengue infections.

Although subjects are asked to come to a study hospital if fever (body temperature $\geq 38^{\circ}\text{C}$ by any route) is sustained for two consecutive days, a subject could present on the first day of fever. In this case the physician may still consider the subject as a suspected dengue case based on medical judgement and collect a blood sample for laboratory diagnosis.

A suspected dengue case presenting at the health care facility within 5 days following the onset of fever (i.e. day of fever onset and the next 4 days) is defined as an 'early presenter'.

A suspected dengue case presenting at the health care facility 6 days or more after the onset of fever will be defined as 'late presenters'.

An example of other signs and symptoms of dengue, associated with fever, include but are not limited to: fatigue, headache, pain behind the eyes, abdominal pain, nausea, vomiting, muscle ache, joint ache, diffuse rash on the trunk, abnormal sensitivity to light (photophobia) and itching of skin (pruritus).

The start date of a suspected symptomatic dengue case is defined by the date of fever or the date of first symptoms which ever appear last. In case both the date of fever and the date of first symptoms are missing, the start date will be the date of visit with symptoms.

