5.7.1.1. Suspected symptomatic dengue case (Amended 16 October 2017)

Febrile illness with body temperature $\geq 38^{\circ}\text{C}$ measured (by any route) on at least two consecutive days and less than 14 days with or without the presence of other dengue symptoms or signs, without an obvious aetiology unrelated to dengue, based on investigator’s judgement.

Although subjects are asked to come to a study hospital if fever (body temperature $\geq 38^{\circ}\text{C}$) *is* sustained for two consecutive days, a subject *could* present on the first day of fever. In this case the physician may still consider the subject as a suspected dengue case based on medical judgement and collect a blood sample for laboratory diagnosis.

Subjects should be examined at the health care facility during the 5 days following fever onset, as this is a requirement for RT-qPCR diagnosis of dengue infection and serotype identification.

However, subjects presenting until 30th (included) day of fever onset will be considered for investigation. After the 30th day, subjects will not be considered as suspected dengue cases.

A suspected dengue case presenting at the health care facility within 5 days following the onset of fever will be defined as an ‘early presenter’.

Subjects presenting for care *between sixth and 30th day* of fever onset will be defined as ‘late presenters’.

An example of other signs and symptoms of dengue, associated with fever, include but are not limited to: fatigue, headache, pain behind the eyes, abdominal pain, nausea, vomiting, muscle ache, joint ache, diffuse rash on the trunk, abnormal sensitivity to light (photophobia) and itching of skin (pruritus).

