6.4. Probable dengue case

- For early presenters, a probable case will be that case without laboratory confirmation, presenting IgG positive in the convalescent sample.
- For late presenters, a probable case will be the case without seroconversion of IgM, presenting at least one IgG positive in one sample (acute or convalescent).

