6.1. Suspected symptomatic dengue case

Febrile illness with body temperature $\geq 38^{\circ}\text{C}$ measured (by any route) on at least two consecutive days and less than 14 days with or without the presence of other dengue symptoms or signs, without an obvious aetiology unrelated to dengue, based on investigator's judgement.

Although subjects are asked to come to a study hospital if fever (body temperature $\geq 38^{\circ}\text{C}$ by any route) is sustained for two consecutive days, a subject could present on the first day of fever. In this case the physician may still consider the subject as a suspected dengue case based on medical judgement and collect a blood sample for laboratory diagnosis.

Subjects should be examined at the health care facility during the 5 days following fever onset, as this is a requirement for RT-qPCR diagnosis of dengue infection and serotype identification.

A suspected dengue case presenting at the health care facility within 5 days following the onset of fever (i.e. day of fever onset and the next 4 days) will be defined as an 'early presenter'.

Subjects presenting for care between sixth and 30th day of fever onset will be defined as 'late presenters'.

An example of other signs and symptoms of dengue, associated with fever, include but are not limited to: fatigue, headache, pain behind the eyes, abdominal pain, nausea, vomiting, muscle ache, joint ache, diffuse rash on the trunk, abnormal sensitivity to light (photophobia) and itching of skin (pruritus).

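### SAP Amendment 1 drops the protocol's 30-day limit on suspected dengue cases without declaring it, and its wording can leave elapsed day 5 in no presenter class

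*SAP*

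**What the plan says.** **Protocol Amendment 4.** Section 5.7.1.1 admits presenters up to and including the 30th day of fever onset, then states: "After the 30th day, subjects will not be considered as suspected dengue cases". Late presenters are those seen "between sixth and 30th day". The glossary gives the late window as 6 to 30 days after onset. Early presentation is within 5 days of onset in both places, with no explanation of whether the onset day counts. Table 12 sets the early sample at 5 days or fewer, and Table 13 starts the late sample beyond 5 days.

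**SAP Amendment 1 (29 October 2019).** Section 1 names Protocol Amendment 4 as its basis, and Section 6.1 opens by invoking the protocol. It explains early presentation as "i.e. day of fever onset and the next 4 days" and defines late presentation as "A suspected dengue case presenting at the health care facility 6 days or more after the onset of fever". Its case classification contains no 30-day limit.

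**Other SAP versions.** The November 2017 SAP for the interim analysis, also written against Protocol Amendment 4, uses "Subjects presenting for care between sixth and 30th day of fever onset" for the late class. The June 2019 SAP, written against Protocol Amendment 3, has the uncapped wording that Amendment 1 repeats.

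**The concern.** Presenter class decides which laboratory criteria apply (SAP Amendment 1, Sections 6.2 and 6.4), so the class boundaries help to decide who enters the incidence numerators.

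At the upper end, a suspected case without a time limit can be counted although the protocol says that the person is not a suspected case. The probable route for a late presenter is wide, since it needs only a case "presenting at least one IgG positive in one sample (acute or convalescent"). At the lower end, a case with no class has no confirmation criteria at all.

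The data are sparse. The SAP reports only 10 PCR-confirmed cases and a low number of dengue episodes, and Section 7.2.2.1 switches to an exact Poisson interval when a site, calendar year or month has no event. One reclassified case can therefore move a cell off zero and change how its interval is computed.

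**Working it through.** The plan gives no figure to reproduce, so the check sets the definitions side by side. Let *k* be the days elapsed from fever onset to presentation, with *k* = 0 on the onset day. Counting onset as day 1, the ordinal day is *k* + 1. Each definition was applied to *k* = 0 to 45, apart from the two tables, whose windows are read off directly.

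| Definition | Early | Late | Unclassified within the window | Excluded as too late |
|---|---|---|---|---|
| SAP Amendment 1, plain reading | 0–4 | 6 and above | 5 | none |
| SAP Amendment 1, onset as day 1 in both sentences | 0–4 | 5 and above | none | none |
| SAP Amendment 1, parenthetical ignored | 0–5 | 6 and above | none | none |
| Protocol glossary, elapsed days | 0–5 | 6–30 | none | 31 and above |
| Protocol 5.7.1.1, onset as day 1 | 0–4 | 5–29 | none | 30 and above |
| November 2017 SAP, onset as day 1 | 0–4 | 5–29 | none | 30 and above |
| Protocol Tables 12 and 13, sample windows | up to 5 | above 5 | none | not stated |

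**Upper end.** Under every reading of SAP Amendment 1, a presenter at *k* = 31 or later stays a late presenter. Under either protocol reading that person is not a suspected case. The fever criterion repeated in SAP 6.1 (less than 14 days) does not supply the limit. It bounds how long the fever lasts, and Protocol 5.7.1.1 states it separately from the 30-day rule. Late presentation is possible by design: routine active contacts need only be monthly (Protocol 5.5.5.3), and the script in Appendix B asks about the past month.

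**Lower end.** The gap at *k* = 5 appears only when the early parenthetical, which counts the onset day, is paired with a late rule read as elapsed days. The criteria in Sections 6.2, 6.4 and 6.5 are written for early and late presenters, so an unclassified case defaults to indeterminate under Section 6.6. That would apply even to a case positive by RT-qPCR or NS1. Table 12 allows such a sample at 5 days.

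**Was the change declared?** Section 10 says that all changes are in Sections 7.1.2, 7.2.2, 7.3.2 and 7.4, and summarised in Section 1. Section 1 drops the tertiary objectives and the additional analyses, and its six numbered items cover PCR and secondary-infection analyses, seroprevalence by visit, seasons, the ATP cohort, medical and vaccination history, and the statistical method. Presenter timing is in none of these places.

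**How much follow-up predates the limit?** The rationale for Protocol Amendment 4 (16 October 2017) says that no maximum interval existed before it. From the table in SAP Section 7, the seasons covered are Rio 4, Manaus 4, Salvador 3, Natal 2 and Campinas 1, so 4 + 4 + 3 + 2 + 1 = 14 site-seasons. Seasons run January to June, so those of 2015 to 2017 ended before the amendment: 3 + 3 + 2 + 1 + 0 = 9 of 14.

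**The case against.** The strongest reply is that this is editorial. Section 6.1 invokes the protocol, and since October 2017 sites should not have opened a suspected case after day 30, so few can be in the data. Most follow-up predates the limit, so cases accepted under the old rule were legitimate at the time. A confirmed late case would need a negative IgM more than 30 days after onset and a positive one about 21 days later, so the effect falls mainly on the probable category, a secondary endpoint. These points stand as reasons to expect a small effect. They do not explain why a SAP citing Amendment 4 omits its limit without saying so.

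On day 5, the reply is that the parenthetical counts onset as day 1, and counting the late rule the same way leaves no gap. The November 2017 SAP pairs the same parenthetical with the sixth day, which supports that reading. This is fair: nothing shows that an unclassified group was intended.

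A reader might infer that the late rule departs from the protocol at both ends. It does not, because its lower bound matches the protocol glossary. Only its pairing with the parenthetical makes the gap. A reader might also infer that almost every presenter after day 30 would become probable, because many subjects were IgG positive at Visit 1. The documents do not support that step: Visit 1 uses an indirect IgG assay and suspected-case visits use a capture assay (Protocol Table 8).

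**Conclusion.** The omission of the 30-day limit is a real, undeclared difference between SAP Amendment 1 and the protocol version it cites. The match with the June 2019 SAP suggests wording carried over when the protocol reference was updated, rather than a deliberate widening, but the documents do not say so.

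The day-5 point is a lesser one: an ambiguity that misclassifies cases only on the plain reading. The protocol is itself not uniform. Elapsed day 5 is early by the glossary and Table 12, but late by Section 5.7.1.1 with onset as day 1. The same two readings differ on whether *k* = 30 is inside the limit.

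The size of either effect cannot be calculated, because the documents give no distribution of time to presentation and no count after day 30. It is probably small. The conclusion rests on the SAP being programmed as written. If the analysis dataset already applies the protocol limit, only the wording needs correction.

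**What to change.** - **Limit.** Restore the 30-day limit in SAP Section 6.1, or list its removal as a change in Section 10 with the reason.
- **Count.** Report the number of suspected cases presenting after day 30, by laboratory outcome. Flag any whose onset day was imputed under Section 11.3.1.
- **Both ways.** Show the incidence results with and without those cases. A single retroactive rule for all years would be debatable, because the limit was introduced only in October 2017.
- **Day count.** Reconcile SAP Section 6.1, the protocol glossary, Protocol 5.7.1.1 and Tables 12 and 13 to one stated convention that leaves no gap. The sponsor should decide whether elapsed day 5 is early or late, and state the choice. This review does not presume the answer.

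The cost is a sentence or two in Section 6.1, an entry in Section 10, a date filter, and one repeat of the incidence tables. No new data are needed.

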6.2. Laboratory-confirmed symptomatic dengue case

Early presenter:

At least one of the following findings must be met for a laboratory-confirmed dengue case:

- Dengue virus identification through RT-qPCR on the acute serum sample
- Dengue virus NS1 positive on acute serum sample through ELISA.
- Anti-dengue IgM seroconversion between acute and convalescent serum samples through ELISA.

Late presenter:

- Anti-dengue IgM seroconversion between acute and convalescent serum samples through ELISA.

Acute and convalescent serum samples are samples taken at the first and follow-up visits for suspected dengue case, respectively.

6.3. Virologically confirmed symptomatic dengue infection

A virologically confirmed symptomatic dengue infection is defined as a dengue case confirmed by RT-qPCR.

6.4. Probable dengue case

- For early presenters, a probable case will be that case without laboratory confirmation, presenting IgG positive in the convalescent sample.
- For late presenters, a probable case will be the case without seroconversion of IgM, presenting at least one IgG positive in one sample (acute or convalescent).

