5.7.1.9. Probable dengue case (Amended 16 October 2017)

- *For early presenters, a probable case will be that case without laboratory confirmation, presenting IgG positive in the convalescent sample.*
- *For late presenters, a probable case will be the case without seroconversion of IgM, presenting at least one IgG positive in one sample (acute or convalescent).*

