7. STATISTICAL ANALYSES

Note that data derivation rules are described in Section 11 and will not be repeated below.

Continuous variables will be summarized with number of non-missing observations, mean, standard deviation (SD), median, minimum, maximum, 25th and 75th percentiles. Categorical variables will be summarized with frequency tables; numbers and percentages for each level will be given.

If an elimination code 900 is attributed, then all the analyses planned to be done on the Total cohort will be done on the Total cohort without subjects with code 900, except Template 5 from EPI-DENGUE-006 BOD BR (116606) TFL (Final analysis) (14-JUN-2019) DRAFT.

The final analysis will be performed on the following study sites using data up to the specified study visits and dengue seasons covered up to study termination:

Region/Study sites name	Initial / Expansion / Replacement cohort	Subject numbers	Study visits covered up to study termination	Dengue season covered up to study termination
Rio	Initial	P - PP	Visit 1 to Visit 6	2015, 2016, 2017, 2018
	Replacement*	PP - PP	Visit 1 to Visit 4	2016, 2017, 2018
Manaus	Initial	PPD - PPD	Visit 1 to Visit 6	2015, 2016, 2017, 2018
	Replacement*	PPD - PPD	Visit 1 to Visit 2	2018
Salvador	Initial	PPD - PPD	Visit 1 to Visit 5	2016, 2017, 2018
Natal	Expansion	PPD - PPD	Visit 1 to Visit 3	2017, 2018
Campinas	Expansion	PPD - PPD	Visit 1 to Visit 2	2018

*only 1 replacement cohort

The following results will be available at the scheduled visits for the following tests:

- Dengue IgG ELISA will be available at Visit 1
- For Visit 2 onwards, Dengue IgG ELISA will be available for subjects with IgG negative at the previous visit.

The following results will be available in case of SDC, for the following tests:

Assays	Result type	Early presenters		Late presenters	
		Acute sample (first visit)	Convalescent sample (follow-up visit)	Acute sample (first visit)	Convalescent sample (follow-up visit)
RT-qPCR	Positive, negative or not typeable DENV type Copies/ml Final classification into positive or negative (used for the dengue case classification)	Yes	TNP	TNP	TNP
NS1 ELISA	Reactive or no reactive	Yes	TNP	Yes	TNP
Dengue IgM ELISA	Reactive or no reactive	Yes	Yes	Yes	Yes
Dengue capture IgG ELISA	Reactive or no reactive	TNP	Yes	Yes	Yes
Hematology / Biochemistry	Numerical results	Yes	TNP	Yes	TNP

TNP = test not performed on the sample as per protocol

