7.2.2. Additional considerations

7.2.2.1. Incidence rate

In light of the low number of dengue episodes, the large number of positive anti-dengue IgG at visit 1 and the number of dengue cases reported outside the season,

1. The analyses of PCR confirmed cases (only 10 cases) and the analyses of secondary dengue infections were removed.
2. The analyses by seroprevalence at each visit were removed,
3. The analyses by season were removed. Only the analyses by calendar year are to be conducted

- 4. Subjects without seroprevalence status at visit 1 were removed from the ATP cohort because serological status of symptomatic/inapparent dengue infections cannot be assessed properly for such subjects
- 5. Planned analyses of medical and vaccination history were removed.
- 6. The statistical method was updated to ignore the household cluster effect and to provide incidence rate with confidence interval in absence of dengue episodes in a calendar year for a study site .

Regarding the last point, the expected annual incidence rate for a cohort of subjects followed over a full calendar will be computed using a log-linear model with the number of dengue events (all cases) as depend variable and the total number of subject-month as offset. The model will include the study site, year and month as independent categorical fixed effects (see below).

The expected annual incidence rate in a study site for each year will be estimated as the average of incidence rate over months

```

proc genmod ;
  class center month year;
  model evt= center year month /
    dist=poisson link=log offset=ln TYPE3;

  ods output Estimates=estimc;
  estimate 'center PPD 2014' intercept 12 center 12 0 0 0 0
    year 12 0 0 0 0
    Month 1 1 1 1 1 1 1 1 1 1 1;
  estimate 'center PPD 2014' intercept 12 center 0 12 0 0 0
    year 12 0 0 0 0
    Month 1 1 1 1 1 1 1 1 1 1 1;
  estimate 'center PPD 2014' intercept 12 center 0 0 12 0 0
    year 12 0 0 0 0
    Month 1 1 1 1 1 1 1 1 1 1 1;
  estimate 'center PPD 2014' intercept 12 center 0 0 0 12 0
    year 12 0 0 0 0
    Month 1 1 1 1 1 1 1 1 1 1 1;
  estimate 'center PPD 2014' intercept 12 center 0 0 0 0 12
    year 12 0 0 0 0
    Month 1 1 1 1 1 1 1 1 1 1 1;
  estimate 'overall 2014' intercept 12 center 2.4 2.4 2.4 2.4 2.4
    y 12 0 0 0 0
    Month 1 1 1 1 1 1 1 1 1 1 1;
  estimate 'center PPD 2015' intercept 12 center 12 0 0 0 0
    year 0 12 0 0 0
    Month 1 1 1 1 1 1 1 1 1 1 1;
  estimate 'center PPD 2015' intercept 12 center 0 12 0 0 0

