7.3.2. Additional considerations

The following parameters will be accounted in the summary:

- Laboratory diagnosis (PCR confirmed, other serologically confirmed, negative, inapparent, undetermined)
- Laboratory schedule (Early/Late)
- Primary dengue diagnosis (Yes/No/missing)
- Clinical diagnosis including severity and hospitalization

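### One capture-IgG-positive result makes an unconfirmed suspected case probable dengue, and SAP Amendment 1 no longer plans the incidence split that would separate new from background IgG

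*SAP*

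**What the plan says.** **Rule.** SAP 6.4 states for early presenters: "For early presenters, a probable case will be that case without laboratory confirmation, presenting IgG positive in the convalescent sample". A late presenter without IgM seroconversion is probable when "presenting at least one IgG positive in one sample (acute or convalescent". Protocol 5.7.1.9 has the same rule ("presenting IgG positive in the convalescent sample"), so SAP Amendment 1 did not introduce it. Under SAP 6.5 a case is negative only if every planned test is negative on both samples.

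**Entry condition.** Only suspected cases are classified. SAP 6.1 asks for fever of at least 38°C on two or more consecutive days and under 14 days, "without an obvious aetiology unrelated to dengue". A physician may accept a subject on the first day of fever. Cases without documented fever are ignored.

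**Assays.** In the SAP section 7 table, the "Dengue capture IgG ELISA" is marked as not performed on the early presenter's acute sample. Protocol Table 8 assigns capture IgG to unscheduled visits and indirect IgG to scheduled visits.

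**Reporting.** SAP 7.2.2.1 cites "the large number of positive anti-dengue IgG at visit 1" among its reasons for change. It says that "the analyses of secondary dengue infections were removed", and it also removes analyses by serostatus at each visit. In 7.3.2 the laboratory item reads "Laboratory diagnosis (PCR confirmed, other serologically confirmed, negative, inapparent, undetermined". A separate item records whether the case was primary (yes, no or missing).

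**The concern.** A single reactive IgG shows that antibody is present. It does not show that the present fever produced it. Where many subjects already carry dengue IgG, a suspected case from another cause can be counted as probable dengue if the subject's capture IgG is reactive from an earlier infection. It cannot then be classed as negative. The protocol's Amendment 4 rationale also acknowledges cross-reaction with Zika antibodies, and SAP 7.4 analyses no tertiary objectives, so no planned Zika analysis offsets this.

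The endpoint at stake is the secondary one: symptomatic dengue counting laboratory-confirmed and probable cases. SAP 7.2.2.1 describes few dengue episodes and only 10 PCR-confirmed cases, so a modest background could be a large share of what is counted. A reader of the results would need to see how many probable cases had IgG before the episode. Amendment 1 does not guarantee that view.

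**Working it through.** **1. The plan's own precision figure, used as a yardstick.** Inputs from Protocol 8.2.2 and 8.2.3: 3 subjects per household, homogeneity 0.4, rate 9 per 1000 person-years.

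- Design effect = 1 + (3 − 1) × 0.4 = 1.8.
- Interval = rate ± 1.96 × √(1.8 × rate / person-years).
- One year, 3322.7 person-years: 9 ± 4.33, giving 4.67 to 13.33 (protocol: 4.7 to 13.3).
- Four years, 8611.3 person-years: 9 ± 2.69, giving 6.31 to 11.69 (protocol: 6.3 to 11.7).

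Both reproduce.

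**2. What evidence of timing the rule uses.**

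- Early presenter: capture IgG on the convalescent sample only. No within-episode change can be observed.
- Late presenter: capture IgG on both samples, but a positive acute sample alone suffices.
- Earlier serostatus: known from indirect IgG at scheduled visits, repeated while negative. SAP 5.1 requires Visit 1 serostatus for the ATP cohort. Section 6.4 does not use it.

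**3. Size of the background.** Let F be the rate of non-dengue suspected cases per 1000 person-years and p the share of them reactive on capture IgG from the past. The background rate is F × p. The documents give neither value, so both are assumptions.

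- To move 9 to 11.7 takes 11.7 − 9 = 2.7 per 1000 person-years, for example F = 30 and p = 0.09 (30 × 0.09 = 2.7).
- With p = 0.02 and F from 10 to 100: 0.2 to 2.0, inside the four-year interval.
- With p from 0.02 to 0.80 and F from 10 to 100: 0.2 to 80. Against 9 true cases that is 0.2/9.2 = 2% to 80/89 = 90% of the total.

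**4. What an earlier-negative requirement would strip out.** Assume F = 50, a share s of 0.5 to 0.9 IgG-positive beforehand, p of 0.05 to 0.80 in those subjects, and 2% false positives in the rest.

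- Current rule, 50 × (s × p + (1 − s) × 0.02): from 50 × (0.025 + 0.010) = 1.75 to 50 × (0.720 + 0.002) = 36.1 per 1000 person-years.
- Earlier negative required, 50 × (1 − s) × 0.02: from 0.1 to 0.5.

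That requirement would also drop true secondary infections, which is why it serves as a reporting row and not as a new definition.

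**5. Reporting, side by side.**

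- The SAP of 14 June 2019 summarised prior-visit IgG for each case class, probable included (7.3), and gave confirmed-or-probable and probable incidence by previous exposure (7.4).
- Amendment 1 removes the secondary-infection and by-visit serostatus analyses. It no longer lists the prior-visit IgG summary, and its new method names only gender and age subgroups besides site and year (7.2.2.1). The model's event count is described only as covering all cases, without naming the classes.
- Amendment 1 keeps the case-level primary item (7.3.2). It still reprints a separate probable incidence from the protocol (7.2.1), which is not on the removal list.

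**The case against.** The strongest reply is that the rule is pre-specified in the protocol, that its label already signals weaker evidence, and that the primary endpoint does not use it. All of that stands. It argues for keeping the definition, and the point here concerns reporting.

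Four stronger readings are tempting, and the documents do not support them:

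- **Any unconfirmed fever becomes probable dengue.** The suspected-case condition in 6.1 excludes fever with an obvious other cause.
- **The endpoint is inflated in proportion to baseline IgG, and so rises with age and site seroprevalence.** Visit 1 positivity is by indirect ELISA and probable status by capture ELISA, so one does not carry over to the other. A footnote tying the ELISA to antibody levels typical of acute secondary infection appears only as deleted text in the amendment log. The current text gives no cut-off and no background positivity, and no proportion positive at Visit 1.
- **Every split was dropped.** The primary item and a separate probable incidence remain. Sections 6.7 and 6.8 also define primary and secondary for probable cases. What is lost is incidence by prior exposure and prior IgG by case class. With no probable class in 7.3.2, a table of probable cases by primary status is not assured.
- **Probable cases will be merged with undetermined ones or omitted.** The list does not say where they go, and the table templates are in a separate file.

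It is also fair that the vaccine programme was stopped (SAP 2.1), which weakens the attack-rate argument. The final analysis is still intended for the study report and public posting (SAP 9.1), so interpretability still matters. The SAP's reason for the removals, few episodes, is sound for modelling. It does not prevent a descriptive count.

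**Conclusion.** The point holds as a gap in interpretation and reporting of the confirmed-or-probable secondary endpoint. The definition lets pre-existing IgG make a case probable, and Amendment 1 does not plan the incidence split that would show how often this happens.

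The amount of background cannot be computed from the documents. It could be negligible if capture reactivity from past infection is rare, or dominant if it is common. The 2.7 per 1000 person-years is only a threshold against the planned precision and rests on the planned rate and person-years. All values of F, p and s above are assumptions. The extent of prior IgG positivity is supported only qualitatively.

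If the modelled event count includes probable cases, the modelled annual rates are exposed in the same way. The SAP leaves that open.

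**What to change.** Keep the protocol definition of probable, and change the reporting.

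- **7.2.2.1:** state which classes the all-cases event count includes. Report probable and confirmed-or-probable incidence twice: once counting only probable cases in class (a), and once counting all probable cases.
- **Exclusive classes.** (a) IgG negative at the preceding scheduled visit with no earlier laboratory-confirmed case (primary, section 6.7), or, for late presenters, capture IgG going from acute-negative to convalescent-positive whatever the earlier serostatus. (b) All other probable cases.
- **7.3.2:** replace the laboratory list with the section 6 classes: laboratory-confirmed (PCR, or NS1/IgM), probable, negative, indeterminate. Keep inapparent infections as a separate row. Cross-tabulate probable cases by the retained primary item.

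The cost is SAP wording and a few table rows, from scheduled-visit and episode results already planned to be available. True secondary infections without a documented IgG change would appear only in the all-probable row, and counts per row will be small.
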